1.2 Rational

1.2.1 Outcome of Acute Myeloid Leukemias after failure of frontline treatment

Acute Myeloid Leukemia (AML) is an aggressive malignant disorder of the bone marrow, characterized by the accumulation of immature white cell precursors in the marrow and blood, ultimately resulting in bone marrow failure with infections and bleeding. Treatment with standard induction including an anthracycline and cytarabine results in complete response rate of 35% to 55% in patients with newly diagnosed AML 60 years old and older¹ and 50% to 90% in younger patients. Despite the high rate of CR, most patients will eventually relapse.

In first relapse, there is no single approach considered standard and treatment is selected based on the age of the patient and the duration of first CR. In patients 60 years old or older, intermediate dose cytarabine alone or in association with another cytotoxic agent (idarubicin, daunorubicin, mitoxantrone or etoposide) is commonly used. Despite substantial variability, the second CR rate generally exceeds 30%^{2,3}. However the median overall survival is \leq 6 months. The prognosis of relapsed AML remains poor, especially in elderly patients. Several investigational agents such as cloretazine, clofarabine, vosaroxin, and elacytarabine have been tested prospectively tested in randomized trial in the settings of patients with AML experiencing early relapse or refractoriness to induction. To date, none of them demonstrated a clear benefit on overall survival and there is no registered drug approved for this indication. Thus there is a strong unmet medical need for this situation

1.2.2 Rational for targeting VEGF/VEGFR pathway in AML

While multiple cytokines promote AML proliferation and survival, vascular endothelial growth factor (VEGF) likely plays an important role as a paracrine and/or autocrine mediator. Greater than 85% of bone marrow biopsies from patients with AML express VEGF significantly higher than normal bone marrows [reviewed in (Kampen, Ter Elst et al. 2013⁴]. VEGF receptors are also commonly expressed on leukemic blasts from patients with AML⁴. In particular, VEGFR-2 protein levels are consistently higher than in normal bone marrow^{5,6}. VEGF isoforms can be detected in the cytoplasm of AML blasts and can be secreted^{7,8}.

Elevated plasma concentrations of VEGF-A have been associated with lower complete remission

rates and inferior survival in AML patients⁹⁻¹¹. High VEGF-C expression has been associated with inferior ex vivo sensitivity to cytotoxic chemotherapy in AML blasts¹². VEGF-C plasma concentrations have been demonstrated to have negative prognostic significance in pediatric and adult AML¹³.

Both VEGF-A and VEGF-C stimulate AML blast proliferation and survival in vitro^{10,14,15}. VEGF signaling in AML leads to activation of Bcl-2, HSP, MAPK and PI3K¹⁵. AML bone marrow biopsies often demonstrate increased micro-vessel density compared to normal bone marrow and AML in remission¹⁶⁻¹⁸. VEGF stimulates osteoblasts and osteoclasts and may lead to remodeling of the stem cell niche¹⁹⁻²¹; to what extent this impacts leukemia stem cells (LSC) is not clear.

VEGF antagonists have demonstrated little clinical activity as monotherapy in relapsed or refractory AML^{16,22,23} or MDS²⁴⁻²⁶. However, VEGF antagonists may contribute significantly to outcomes in combination with cytotoxic drugs²⁷⁻³⁰. In timed sequential chemotherapy, AML patients receive a planned second exposure to chemotherapy shortly after their first exposure at a time point planned to coincide with the peak of cytokine-stimulated regrowth of residual leukemia cells. This approach led to superior leukemia-free survival in a pediatric population³¹ as well as in an adult population³² (French). However, timed sequential therapy has led to longer aplasia duration than a single cycle of “seven plus three” (cytarabine plus anthracycline) and has not been widely adopted. Building on this model, Karp and colleagues³⁰ studied a three day infusion of cytarabine in combination with mitoxantrone in patients with relapsed and refractory AML. Historical experience with this combination indicated that remissions were not likely with these drugs alone.

The VEGF inhibitor bevacizumab was administered on day 8, in lieu of the second drug exposure in the timed sequence (Figure 1):

[figure not shown]

Figure 1. VEGF inhibition in a timed sequential chemotherapy model of AML9 (Attached)

Of 49 patients treated, 15 had primarily refractory disease, 12 were refractory to at least two induction regimens, or to reinduction after first relapse; 18 were in first relapse. Toxicities were as expected with intensive reinduction therapy; additional AEs attributed to the known toxicity profile of bevacizumab were observed. 7 patients experienced induction death.

Importantly, residual leukemia was morphologically detectable in 38/48 patients on day 8 prior to bevacizumab. On Day 15 (one week following bevacizumab), 28/48 patients had cleared morphologic leukemia. 16 patients achieved complete remission, including 2/3 newly diagnosed poor-risk AML, 9/18 patients in first remission, and 5/27 patients with primary refractory disease. 7 patients achieved PR, for an overall response rate of 48% following one cycle of treatment. VEGF receptor FLT-1 on bone marrow cells was greater than in normal bone marrow in 12/13 patients examined. On day 8, blasts continued to express FLT-1 in 8/10 patients. Serum free-VEGF was detectable in 14/21 patients prior to treatment (median concentration 12 pg/mL). Day 8 concentrations were higher than on day 0 in 11 patients including 4 patients in whom VEGF had been undetectable, while VEGF concentration had decreased in 6.

Among 15 patients in whom serum was sampled two hours following bevacizumab infusion, 10 had complete suppression of detectable VEGF, while 4 patients had VEGF concentrations ranging from 24 – 82% of the pre-bevacizumab baseline. Sequential examination of bone marrow microvessel density revealed significant decreases in 8/11 patients.

This study confirmed the widespread expression of VEGF in patients with relapsed and refractory AML, and suggested that effective VEGF inhibition could substitute for a toxic second administration of chemotherapy drugs in a timed sequential chemotherapy model, leading to a very promising response rate. This combination was not further developed due to lack of priority from the manufacturer of bevacizumab, despite great interest from the Johns Hopkins group and the Cancer Therapy Evaluation Program. (Personal communication).

1.2.3 Nintedanib, an oral VEGF inhibitor

Nintedanib^{33,34} is an orally bioavailable VEGFR inhibitor with an IC50 ranging from 100 – 300 nM. Nintedanib also inhibits the different isoforms of FGF and PDGFR. In a trial in lung cancer in combination with paclitaxel and carboplatin in non-small cell lung cancer³⁵, mean Cmax was 63 ng/mL, similar to that in monotherapy trials³⁶⁻³⁹ and in combination with docetaxel in prostate cancer patients. Nintedanib administration was associated with decrements in plasma soluble VEGFR2.

Nintedanib is being investigated in several cancer indications⁴⁰. Two completed phase III NSCLC^{35,41} studies and one phase III in ovarian cancer is still ongoing; the development for colorectal cancer, renal cell carcinoma, and hepatocellular carcinoma is in phase II. Additionally, nintedanib is also registered for the non-cancer indication idiopathic pulmonary fibrosis (IPF)^{42,43} (150mg bid). As of 15 Apr 2014, a total of 3470 cancer patients, 143 healthy volunteers and 1529 patients with IPF have been treated with nintedanib. Among the cancer patients, 672 were treated with monotherapy, 1255 with combination of nintedanib and various backbone therapies, 162 with the combination of afatinib⁴⁴, an EGFR/HER2 inhibitor, approved in the treatment of patients with NSCLC carrying EGFR mutation and 30 patients with the combination of volasertib, a PLK1 inhibitor. 1351 patients were treated with either nintedanib or nintedanib-matching placebo in ongoing blinded studies.

Based on the phase I dose escalation trials³⁶⁻³⁹, the MTD (maximum tolerated dose) was determined to be 250 mg bid for twice daily dosing in Caucasians and 200 mg bid in Japanese patients⁴⁵ with a

manageable safety profile in advanced cancer patients. The predominant adverse events were nausea, diarrhea, vomiting, abdominal pain and fatigue of mostly low to moderate severity. Dose limiting toxicities (DLT) were mainly confined to reversible hepatic enzyme elevations (AST, ALT, γ -GT) which increased dose-dependently. Most cases occurring at doses of 250 mg and above, and a very low incidence at doses below 200 mg and were reversible after discontinuation of nintedanib treatment. All adverse events observed after single administration of single doses of nintedanib to healthy volunteers were only of CTCAE grade 1 severity and fully reversible.

1.2.4 *Combination of chemotherapy and Nintedanib in relapsed/refractory AML*

The availability of an orally bioavailable VEGF inhibitor with tolerable toxicity profile provides an opportunity to follow the signal from the bevacizumab study in the development of VEGF inhibition in reinduction therapy. The tolerability of the combination will be confirmed in a short phase Ib followed by a randomized phase II study evaluating the potential benefit of such a combination as compared to convention care. An adaptive design will be used for the randomized part. This will allow to quickly conclude on the potential lack of efficacy of any of the arm of the study as compared to historical controls.

1.3 Objectives

1.3.1 *Primary objective*

Phase I: To determine the safety and tolerability of Nintedanib in combination with intensive AML chemotherapy; Idarubicin and cytarabine after 1 cycle of treatment

Randomized Phase II: To determine the complete remission rate (CR+ CRp) of chemotherapy ; Idarubicin and cytarabine + nintedanib compared to chemotherapy Idarubicin and cytarabine +placebo after 1 cycle of treatment

1.3.2 *Secondary Objectives*

To determine overall response rate of nintedanib+ chemotherapy as compared to placebo + chemotherapy

To determine the overall survival and leukemia free survival of patients treated with nintedanib+chemotherapy as compared to placebo+chemotherapy.

To determine the percentage of patients bridging to allogeneic transplantation as well as time to transplantation after nintedanib+chemotherapy as compared to placebo+chemotherapy

To determine hematological response rate of the nintedanib+ chemotherapy as compared to placebo + chemotherapy

Phase II: To determine the safety and tolerability of nintedanib+chemotherapy as compared to placebo+chemotherapy

1.3.3 Exploratory objectives

To determine the role and correlate biomarkers of nintedanib activity in relapse/refractory AML (see below)

1.4 Endpoints

1.4.1 Primary endpoint

Phase I: Safety evaluated according to NCI CTCAE V4.03 criteria

Phase II: Complete remission rate (including CR and CRp) evaluated according to IWG AML 2003 criteria after 1 cycle of treatment

1.4.2 Secondary endpoints

Overall response rate will be defined according to IWG 2003 criteria⁴⁶ and includes: CR, CRp, CRI, PR, and marrow leukemia free state (MLFS). Rates of hematological improvements (as defined by IWG 2006 Myelodysplastic syndromes criteria⁴⁷) will also be recorded.

Overall Survival will be defined from time of treatment initiation to the time of last follow-up or death. Survival with censoring patients at the time of transplantation will also be evaluated.

Leukemia free survival will be defined from time of documentation of complete remission (CR+CRp+CRI) to the time of last follow-up, relapse, or death of any cause. Survival with censoring patients at the time of transplantation will also be evaluated.

1.5 Treatment Plan

1.5.1 *Global treatment strategy*

Phase I: This is an initial exploratory phase to confirm the safety and tolerability of the combination of Nintedanib+chemotherapy. The AML chemotherapy induction and consolidation regimen occur at an inpatient hospital stay typically averaging 5 weeks and is Standard of Care (SOC) per local hospital policy. The induction and consolidation regimen combines Idarubicin 12mg/m²/d IV push over 10-15 minutes days 1 to 3 and Cytarabine 0.667g/m²/d (24 hr. IV infusion) day 1 to 3. During Phase I, all patients will receive the combination chemotherapy in addition to Nintedanib 200mg bid starting at Day 8 through day 28 (end of cycle). If a significant incidence of dose limiting toxicities is demonstrated, Nintedanib will be given at a lower dose level (150mg bid). Patients may be discharged based on local site SOC and re-admitted prior to the start of the next cycle however, some patients will stay in the hospital continuously (especially between the first two induction cycles). Induction cycle 2 can begin as early as study day 29 regardless of count recovery status if the investigator believes it would be clinically beneficial. Patients can be given a “break” between cycles of induction based on investigator’s clinical judgement and clinical response. Count recovery is necessary before a consolidation cycle can begin. If count recovery is not achieved 60 days after Cycle 1 Day 1, the patient is removed from the study.

Phase II: Based on the phase I dose, in the randomized phase II, the combination of chemotherapy + Nintedanib will be compared with chemotherapy+placebo. The AML chemotherapy induction and consolidation regimen occur at an inpatient hospital stay typically averaging 5 weeks and is Standard of Care (SOC) per local hospital policy. The induction and consolidation chemotherapy regimen for Phase II are identical to that in Phase I and combines Idarubicin 12mg/m²/d IV push over 10-15 minutes days 1 to 3 and Cytarabine 0.667g/m²/d (24 hr. IV infusion) day 1 to 3. In Phase II, patients will be randomized to receive the combination chemotherapy in addition to Nintedanib (dose determined in Phase I) at Day 8 through day 28 (end of cycle) or placebo at Day 8 until day 28 (end of cycle). Patients may be discharged based on local SOC and re-admitted prior to the start of the next cycle however, some patients will stay in the hospital continuously (especially between the first two induction cycles). Induction cycle 2 can begin as early as study day 29 regardless of count recovery status if the investigator believes it would be clinically beneficial. Patients can be given a “break” between cycles of induction based on investigator’s clinical judgement and clinical response. Count recovery is necessary before a consolidation cycle can begin. If count recovery is not achieved 60 days after Cycle 1 Day 1, the patient is removed from the study. **Figure 2.** describes the overall

strategy of the Phase II portion of the study. All patients will be evaluated for response based upon count recovery or following day 45, whichever comes first. Patients without count recovery and without signs of bone marrow leukemia at day 45 will be followed up to day 60. If no recovery is observed at day 60, patients will be removed from protocol and considered a failure.

In phase I, patients who fail to achieve CR or CRp based on IWG 2003 AML response criteria (pg. 77) after first cycle of treatment may receive a second cycle of treatment using Nintedanib+ chemotherapy. Patients who achieve CR or CRp after one or two induction cycles may receive up to 2 cycles of consolidation using the same regimen.

In phase II, patients failing to achieve response based on IWG 2003 AML response criteria after cycle 1 will be unblinded, and all those who had been receiving placebo will be offered a cycle of Nintedanib+ chemotherapy (cross over). Patients in the Nintedanib arm may receive a second induction cycle of Nintedanib. Based on clinical judgement, patients can receive up to 2 cycles of consolidation after induction cycle (s) are complete.

Patients are eligible for allogeneic transplantation as soon as remission is achieved and a donor is identified. All transplant procedures occur off study. For responding patients not eligible for transplantation, maintenance therapy with Nintedanib/Placebo will be provided until documented progression.

Patients should NOT start Cycle 1 day 1 on a Thursday or Friday in order to facilitate sample collection, processing and shipment to Sponsor to avoid weekend deliveries.

[figure not shown]

Figure 2. Global treatment strategy of the Phase II portion of the study

NIN/PLA: Nintedanib/ Placebo, CR: complete response, CRp: CR with incomplete counts recovery. Patients can receive up to 2 induction and 2 consolidation cycles.

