1.1 Trial summary

Title	A phase I-II trial of a combination of Nintedanib, an oral VEGF inhibitor, in combination with induction chemotherapy for patients with refractory or first relapse acute myeloid leukemia
Indication	Treatment of patients with relapsed/refractory AML as defined by the WHO
Design	Phase I- randomized II study
Sponsor	YALE UNIVERSITY
Contact	[name] PhD [contact] [contact] Email: [contact]
Products	Nintedanib/ placebo, idarubicin, cytarabine
Summary of Rationale	Nintedanib is an oral VEGF inhibitor with a good tolerance profile. There is evidence of a potential clinical impact of VEGF inhibition in AML and some in vitro evidence of activity of Nintedanib against AML blasts. Given that outcome of relapse/refractory AML patient is poor and that no standard option is available for this group of patients, we anticipate that a combination of nintedanib+ induction chemotherapy may be an effective strategy for this group of patients.
Treatment plan	
Phase I: Patients who meet eligibility criteria and sign informed consent will receive the following during an inpatient hospital stay; Idarubicin 12mg/m²/d IV Push over 10-15 minutes days 1 to 3, cytarabine 0.667g/m²/d (24 hr.) IV infusion day 1 to 3 and Nintedanib 200mg BID PO day 8-28. There will be no drug administered on days 4-7. Length of inpatient hospital stay is based on local site SOP.
 
Phase II: Patients who meet eligibility criteria and sign informed consent will receive the following during an inpatient hospital stay; Idarubicin 12mg/m²/d IV Push over 10-15 minutes days 1 to 3, cytarabine 0.667g/m²/d (24 hr.) IV infusion day 1 to 3 and Nintedanib 200mg BID PO on day 8-28 OR placebo. There will be no drug administered on days 4-7. Length of inpatient hospital stay is based on local site SOP.
 
For both Phase I and II, a maximum of 2 induction and 2 consolidation cycles may be given, cycles are 28 days.
 
During Phase II, all Patients failing to achieve response based on IWG 2003 AML response criteria after cycle 1 will be unblinded, and all those who had been receiving placebo will be offered Nintedanib+ chemotherapy (cross over) for cycle 2. Patients in the Nintedanib arm can be given a second cycle of Nintedanib.
 
Nintedanib maintenance treatment will be given to responding pts not eligible for Hematopoietic stem cell transplantation (HCT) for up to two years or until disease progression. Patients eligible for HSCT will be taken off study prior to HSCT.

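### The 60-day removal clock runs from Cycle 1 Day 1 with no provision for a second induction, so second-cycle patients still without count recovery can be removed before, or within days after, the end of cycle 2

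*Combined protocol and SAP*

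**What the plan says.** **Removal.** Section 1.5.1 carries the same sentence in its Phase I and Phase II paragraphs: "If count recovery is not achieved 60 days after Cycle 1 Day 1, the patient is removed from the study". For Phase II a further sentence takes patients unrecovered at day 60 off protocol and counts them as failures.

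**Second induction.** The trial summary (1.1) allows "a maximum of 2 induction and 2 consolidation cycles may be given, cycles are 28 days". Section 1.5.1 adds "Induction cycle 2 can begin as early as study day 29 regardless of count recovery status", if the investigator sees clinical benefit, and "Patients can be given a “break” between cycles of induction based on investigator’s clinical judgement and clinical response". No maximum length is given for that break.

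**Evaluation.** "All patients will be evaluated for response based upon count recovery or following day 45, whichever comes first". Then: "Patients without count recovery and without signs of bone marrow leukemia at day 45 will be followed up to day 60". Neither sentence names the cycle it refers to.

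**After cycle 1 failure.** In Phase II, placebo non-responders are unblinded and offered a cycle of nintedanib plus chemotherapy. For the other arm, "Patients in the Nintedanib arm may receive a second induction cycle of Nintedanib". Consolidation may follow the induction cycle or cycles, but only after count recovery. The Phase I text is explicit: "Patients who achieve CR or CRp after one or two induction cycles may receive up to 2 cycles of consolidation using the same regimen".

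**Other 60-day text.** Section 1.6 makes non-recovery at day 60 without morphologic leukemia a hematologic DLT. Section 1.18.1 follows Phase I patients for 60 days from the last study drug administration. It then calls sixty days the longest wait before removal, without naming a start for that wait.

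**The concern.** The removal sentence and the second-induction provisions sit in the same paragraphs, but the clock was not adapted to a second cycle. A patient may be re-induced precisely because cycle 1 failed, may lack count recovery at that moment with the protocol's permission, and is then removed for lacking recovery by a date counted from the first cycle. For most permitted start dates, that date falls while cycle 2 study drug is still scheduled.

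What is at stake is everything that depends on cycle 2: response to re-induction and to crossover, cycle 2 safety experience, the route to consolidation, and leukemia-free survival, which by section 1.4.2 begins only at a documented remission. A slow remission after cycle 2 could be recorded as a non-response or not recorded at all. Sites applying the sentence literally would also produce different data from sites treating it as a cycle 1 rule.

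**Working it through.** **Inputs.** Cycle length is 28 days (1.1). Study drug is given on days 8 to 28, so 21 days per cycle (1.1, 1.5.1). The removal limit is study day 60 from Cycle 1 Day 1, the earliest cycle 2 start is study day 29, and evaluation may be as late as day 45 (all 1.5.1). Design response rates are 15% and 40%, with a stopping table running from 8 to 24 patients per arm (1.7).

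**Plan's own figure.** Earliest cycle 2 start = 28 + 1 = study day 29, which agrees with the protocol.

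**Where the limit falls in cycle 2.** Let s be the study day of cycle 2 day 1.
- Cycle 2 day reached on study day 60 = 60 − s + 1.
- Study day of cycle 2 day 28 = s + 27.
- Cycle 2 study-drug days given by day 60 = min(28, 60 − s + 1) − 7, not below 0.

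| Cycle 2 start (study day) | Cycle 2 day on study day 60 | Study day of cycle 2 day 28 | Study-drug days given, of 21 |
|---|---|---|---|
| 29 | 32 | 56 | 21 |
| 33 | 28 | 60 | 21 |
| 35 | 26 | 62 | 19 |
| 46 (day after a day-45 evaluation) | 15 | 73 | 8 |
| 60 | 1 | 87 | 0 |

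Cycle 2 day 28 falls by study day 60 only if s + 27 ≤ 60, so s ≤ 33. If the limit is read as Cycle 1 Day 1 plus 60 days (study day 61), every cycle 2 day in the second column moves by one and the latest start is day 34.

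**Recovery time allowed.** Cycle 1 has up to 60 days from its Day 1. Cycle 2 has at most 32. A 45-day evaluation window counted from cycle 2 day 1 would need s + 44 ≤ 60, so s ≤ 16, which is impossible when the earliest start is day 29.

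**The period in section 1.18.1.** Taking day 28 as the last cycle 1 dose, 60 days after it is study day 28 + 60 = 88. That is 28 days later than the limit in section 1.5.1.

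**The end-of-treatment work-up.** Section 1.10.4 allows it up to 30 days after the last nintedanib dose. For a day-29 start with the last dose on study day 56, the window runs to 56 + 30 = study day 86, beyond the removal day.

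**Ceiling on numbers.** Running the stopping table exactly, with each response known before the next patient enters, gives an expected arm size of 11.27 at 15% and 11.52 at 40%. Expected cycle 1 failures:
- placebo: 0.85 × 11.27 = 9.6;
- nintedanib: 0.60 × 11.52 = 6.9.

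If both arms run to 24, these become 0.85 × 24 = 20.4 and 0.60 × 24 = 14.4. All four figures count every cycle 1 failure, not only those who start cycle 2 without count recovery.

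**The case against.** The strongest reply is that the rule was never meant for re-induced patients. The sentence on days 45 to 60 concerns patients without marrow leukemia, and sections 1.6 and 1.18.1 attach the day-60 DLT to the same condition. Read together, they suggest a limit on prolonged aplasia after cycle 1. That reading is plausible, but the removal sentence itself carries no such restriction, so a site cannot be sure of it.

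A reader might also infer that all crossover and second-cycle patients leave before cycle 2 can be assessed. The documents do not support that. Removal depends on absent count recovery. A non-responder who recovered counts with persistent leukemia is not clearly caught, although the text does not say whether recovery must be shown again in cycle 2. Starts on days 29 to 33 reach cycle 2 day 28 by day 60, and the cycle 2 calendar has blood counts three times weekly. Nor do the documents say how often cycle 1 failures lack recovery when cycle 2 begins, so the failure counts cannot be read as counts of removed patients.

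The harm is partly limited already. The primary endpoint is read after one cycle (1.4.1). Section 1.15 asks, where feasible, for the usual follow-up of patients who stop early. Section 1.19.9 collects adverse events for 30 days after nintedanib stops. Section 1.18 gathers relapse, subsequent therapy and death. But the follow-up in section 1.18 is by telephone, ends at subsequent anti-cancer therapy and does not list response, so it would not recover a late cycle 2 remission.

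Finally, the Phase II arms are not powered for comparison, and crossover mixes them after cycle 1. Unequal loss between arms is therefore a secondary worry.

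**Conclusion.** The point holds as a conflict between a stated rule and the provisions around it. The clock is tied to Cycle 1 Day 1 and never reset. Followed literally, second-induction patients still without count recovery are removed on cycle 2 day 32 at the latest, and before cycle 2 day 28 for any start after day 33 (day 34 on the alternative day count). Section 1.18.1 adds a second 60-day period with a different starting point.

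The complete remission rate after cycle 1 and its stopping table are not affected. Exposed are cycle 2 and crossover response and safety data, entry to consolidation, and leukemia-free survival. How many patients are involved cannot be estimated from the documents. They are a subset of cycle 1 failures: about 10 placebo and 7 nintedanib patients expected at the design rates, or 20 and 14 only if both arms reach 24. The lower pair assumes no accrual while responses are pending, so true arm sizes could lie between. Both pairs include patients who die in induction, recover counts or never start cycle 2.

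This rests on the text alone. Figure 2, the Phase II treatment scheme, was not available and could not be checked.

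**What to change.** Reconcile section 1.5.1 (the Phase I and Phase II removal sentences, the day-45 and day-60 sentences, and the second-induction and crossover text) with sections 1.6 and 1.18.1. The amended text should state:

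1. which cycle's Day 1 starts the 60-day clock for a patient who has begun cycle 2;
2. whether the rule applies only to patients without marrow leukemia, and whether recovery shown in cycle 1 must be shown again in cycle 2;
3. how the 60 days after last study drug in section 1.18.1 relate to the limit in section 1.5.1.

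The clinical rule is the sponsor's to decide; the passages only need to agree.

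Separately, state that day 60 without recovery fixes the cycle 1 result as a failure but does not end collection of cycle 2 response, relapse, transplant and survival data, and add response to the items listed in section 1.18.

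The cost is a wording amendment, with no new type of assessment. The downside is that a few patients stay under data collection longer.
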